5.5.2 Dose Limiting Toxicity (DLT)

The DLT definition is described in section 4.2 of the protocol. A patient data listing will be provided for all DLTs, if any.

5.5.6 Laboratory Data

The following laboratory parameters are measured at visits specified in the Schedule of Assessments (Table 3 and Table 6).

Laboratory Panel	Test Parameters
Hematology	White Blood Cells: White Blood Cells, Basophils Absolute, Basophils Percent, Eosinophils Absolute, Eosinophils Percent, Lymphocytes Absolute, Lymphocytes Percent, Monocytes Absolute, Monocytes Percent, Neutrophils Absolute, Neutrophils Percent, Bands Absolute*, Bands Percent*, Metamyelocytes Absolute*, Metamyelocytes Percent*, Myelocytes Absolute*, Myelocytes Percent*, Blasts Absolute*, Blasts Percent*, Lymphocytes Atypical Absolute, Lymphocytes Atypical Percent, Plasma Cells Absolute, Plasma Cells Percent, Promyelocytes Absolute*, Promyelocytes Percent*, WBC Morphology,
	Red Blood cells: Red Blood Cells, Hemoglobin, Hematocrit, Mean Cell Volume, Mean Corpuscular Hemoglobin, Mean Corpuscular Hgb Concentration Red Cell Distribution Width, Nucleated RBC Manual Absolute*, Nucleated RBC Manual Percent*, Retic AA, Retic PA, RBC Morphology
Coagulation	PT, INR and aPTT
Serum Chemistry	Liver function: Aspartate aminotransferase (AST), Alanine aminotransferase (ALT), Total bilirubin (TBL), Direct bilirubin, Indirect bilirubin, Alkaline phosphatase (ALP), Albumin, Total Protein,
	Renal function: Creatinine, Urea,
	Electrolytes and minerals: Sodium, Chloride, Calcium, Phosphate, Potassium,
	Metabolism: Glucose (random), Creatinine phosphokinase (CPK)
Urinalysis	pH, Specific gravity, Protein, Glucose, Ketones, Bilirubin, Blood, Nitrites, Urobilinogen, Leukocytes,
T/B/NK/monocyte counts	CD3, CD4, CD8, CD14, CD19, CD16/56 and B cell subsets (i.e. naïve, memory and plasmablasts)

^{*}Summary statistics and shift tables will not be provided for the hematology parameters indicated because they were not consistently assessed for all patients

Shifts from baseline tables will be provided for the laboratory parameters where abnormality (ie, out of normal range) and/or clinically significant abnormality can be determined.

The maximum and minimum values of all post-baseline visits will be summarized.

A special group of clinical laboratory tests, including ALT, AST, TBL and ALP, which are believed to be the indicators for drug induced liver injury (DILI) will be assessed separately. Frequency tables will be used to summarize elevations in these parameters. The following criteria will be documented:

- AST > 3x, 5x, 10x and 20x Upper Limit of Normal (ULN)
- ALT > 3x, 5x, 10x, and 20x ULN
- Total Bilirubin > 1.5x and 2x ULN
- ALP > 1.5x ULN
- ALT or AST > 3x ULN and Total Bilirubin > 1.5x ULN
- ALT or AST > 3x ULN and Total Bilirubin > 2x ULN

Scatter plots of the peak TBL divided by the ULN will be plotted on a log scale against the peak ALT divided by the ULN. Reference lines will be plotted for the ULN for TBL and ALT, 2x ULN for TBL and 3x ULN for ALT. Any patients in the upper right quadrant, which is defined by 2x ULN for TBL and 3x ULN for ALT, would represent cases to be investigate for potential DILI.

Patient data listings will be provided for patients with abnormal CS values (or out-of-normal range values as needed) at any visits.

5.5.7 Vital Signs and Body Weight

Vital signs include blood pressures (BP), pulse, temperature and respiratory rate and body weight are measured at visits specified in the Schedule of assessments (Table 3 and Table 6).

The observed values and change from baseline values will be summarized by visit for each starting dose and overall.

The following ranges will be used to classified the BP and pulse measurements as Low/Normal/High:

- Systolic blood pressure (SBP): 90 to 140 mmHg, inclusive
- Diastolic blood pressure (DBP): 60 to 80 mmHg, inclusive
- Pulse: 50 to 100 bpm, inclusive

Shift from baseline tables will be produced by using the above criteria and the maximum post-baseline values.

Descriptive statistics tables will be generated for the vital sign measurements taken during the main and LTE period.

Patient data listings will be provided patients with out-of-range SBP, DBP or pulse results at any visits.

5.5.8 12-Lead ECG

Single ECG assessment is performed at the Screening, End of Study, Early Withdrawal and Unscheduled visit. Triplicate ECG assessments are performed at pre-dose and at 2 hours post-dose (+/- 15 minutes) on the first day of dosing at each new dose level. For patients continue into a new cycle at the prior dose level, ECG is not required.

The ECG parameters include: heart rate, QT interval, P-R interval, RR interval, QRS duration, QTcF interval and overall ECG assessments (normal, abnormal – not clinically significant (NCS) and abnormal – clinically significant (CS)).

For triplicate ECG assessments, the average of the three numerical values and the worst of the three overall ECG assessments will be used for the summary statistics.

For the numerical values, observed and change from baseline will be summarized by descriptive statistics.

For overall ECG assessments, shift from baseline tables will be for the worst post-baseline assessments.

Descriptive statistics tables will be generated for data collected during the main and LTE period.

A patient data listing will be provided for patients with abnormal CS ECG assessments at any visits.

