3.4.3 Study Visits

For protocol version 7.0, the study visits are:

- Screening
- Cycle X Day 1, Cycle X Day 8, Cycle X Day 15 and Cycle X Day 22, where X <= 3
- Day 85 (Last day of active rilzabrutinib treatment)
- Day 113 (Follow-up visit)
- Day 141 (Follow-up visit)
- Day 169 (End of Study visit)
- Early Withdrawal
- Unscheduled visit
- Laboratory Only Visits for Hematology, differential & retics: Days 92, 99, 106, 120, 127, 134, 148, 155, 162 and 169) (Follow-up visit)

For protocol version 8.0, the study visits are:

- Screening
- Cycle X Day 1, Cycle X Day 8, Cycle X Day 15 and Cycle X Day 22, where X ≤ 6
- Day 169 (Last day of active rilzabrutinib treatment)
- Day 197 (End of Study visit)
- Early Withdrawal
- Unscheduled visit
- Laboratory Only Visits for Hematology, differential & retics: Days 176, 183 and 190) (Follow-up visit)

For protocol version 9.0 to version 14.0, the study visits are:

- Screening
- Cycle X Day 1, Cycle X Day 8, Cycle X Day 15 and Cycle X Day 22, where X ≤ 10
- LTE: LTE Cycle X Day 1, LTE Cycle X Day 8, LTE Cycle X Day 15 and LTE Cycle X Day 22, where X ≤ 6
- LTE monthly visit: LTE Cycle X Day 1, where $7 \le X \le 12$
- LTE every 3 months visit: LTE Visit X, where $X \ge 1$ (until patients no longer on study)
- Last day of active rilzabrutinib treatment
- End of Study
- Early Withdrawal
- Unscheduled visit
- Laboratory Only Visits for Hematology, differential & retics: Days 176, 183 and 190) (Follow-up visit)

All scheduled visits will be used for descriptive summary. Unscheduled visits will be included in the derivation of 'Last value on-treatment' defined in section 3.4.4.

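### Part A vital-sign shift tables use only the maximum post-baseline value, so the Low column misses most falls in blood pressure and pulse

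*SAP*

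**What the plan says.** Part A SAP 5.5.7 sets two-sided categories: "The following ranges will be used to classified the BP and pulse measurements as Low/Normal/High". The ranges are "Systolic blood pressure (SBP): 90 to 140 mmHg, inclusive", "Diastolic blood pressure (DBP): 60 to 80 mmHg, inclusive" and "Pulse: 50 to 100 bpm, inclusive". Low therefore means systolic below 90 mmHg, diastolic below 60 mmHg or pulse below 50 bpm.

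The rule that fills the table follows: "Shift from baseline tables will be produced by using the above criteria and the maximum post-baseline values". The section names no shift table by minimum or by worst value.

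The same section also plans observed values and changes from baseline by visit, for each starting dose and overall, and a listing: "Patient data listings will be provided patients with out-of-range SBP, DBP or pulse results at any visits".

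Nearby text is worded differently. Shift tables for the overall ECG assessment (5.5.8) and for physical examination (5.5.9) use the worst post-baseline result. For laboratory data, 5.5.6 says: "The maximum and minimum values of all post-baseline visits will be summarized". Protocol 10.10.3 flags vital signs in both directions. The Part B SAP (4.7.3.1 and Appendix 4) uses the worst value, with separate low and high criteria for heart rate, systolic and diastolic pressure.

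**The concern.** The table offers a Low category but fills it with the one statistic least able to reach it. For High, the patient is represented by the most extreme reading in that direction. For Low, the same patient is represented by the least extreme one. A reader who sees a near-empty Low column would naturally conclude that patients did not become hypotensive or bradycardic, when the table could hardly have shown it.

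Safety and tolerability is a Part A objective, and the protocol's primary safety endpoint includes clinically significant changes in vital signs. No other planned vital-sign table counts how many patients went Low. By-visit summaries describe distributions, and the listing has no denominator.

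**Working it through.** The plan gives no figure on this point, so there is nothing to reproduce. The direction follows from the definition of a maximum; the calculation shows only the size.

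**Visits.** SAP Table 4 (protocol version 8 onward) schedules vital signs on Day 1 and Day 15 of each cycle, Day 169 and Day 197. Section 3.4.3 gives the version 8 cycles as "Cycle X Day 1, Cycle X Day 8, Cycle X Day 15 and Cycle X Day 22, where X ≤ 6"; the Day 8 and Day 22 visits are laboratory only. Post-baseline vital-sign visits: Day 1 of cycles 2–6 (5) + Day 15 of cycles 1–6 (6) + Day 169 + Day 197 = 13. The same count from Table 3 (version 7) gives about 12.

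**Independent visits.** If each reading is Low with probability p, then P(any Low) = 1 − (1 − p)^13 and P(maximum Low) = p^13.

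- p = 0.10: 1 − 0.9^13 = 74.6%, against 0.1^13 = 10^-13.
- p = 0.50: 99.99%, against 0.5^13 = 0.012%.

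**Correlated visits.** Each reading is N(μ − δ + b, (1 − ρ)σ²), with patient effect b ~ N(0, ρσ²), sustained fall δ (zero at baseline) and lower limit L. Let p(b) = Φ((L − μ + δ − b)/(σ√(1 − ρ))), and let q(b) be the probability that the baseline reading is not Low. Then:

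- share with any Low reading = E[q(1 − (1 − p)^13)] / E[q]
- share shown as Low by the maximum = E[q p^13] / E[q]

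The limits L come from 5.5.7. My assumptions are: systolic mean 120, SD 12; diastolic 75, SD 8; pulse 70, SD 10; and ρ from 0.3 to 0.8. In each cell, the first range is any Low reading and the second is shown as Low. The first falls and the second rises as ρ goes from 0.3 to 0.8.

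| Sustained fall | Systolic | Diastolic | Pulse |
|---|---|---|---|
| 0 | 6.4–2.5% / 0–0.002% | 23.7–8.8% / 0–0.014% | 19.0–7.0% / 0–0.010% |
| 10 | 34.3–15.6% / 0–0.2% | 85.5–53.7% / 0.1–4.7% | 69.9–37.8% / 0.02–1.6% |
| 20 | 78.0–45.9% / 0.05–3.9% | 99.8–92.8% / 13.1–43.2% | 97.6–78.4% / 2.0–19.3% |
| 30 | 97.7–78.8% / 2.2–20.6% | 100–99.8% / 74.5–88.4% | 100–96.9% / 28.6–59.9% |

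At ρ = 0.5 with no fall, the any-Low shares are 5.0%, 17.7% and 14.3%. A 20 mmHg diastolic fall shows as Low in 23.0% of patients, and a 30 mmHg fall in 80.0%.

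**Fewer visits.** A separate simulation restricted to patients Normal at baseline used 5 visits, no drug effect, correlation 0.3 to 0.9 and somewhat different means and SDs (systolic 122, 14; diastolic 75, 9; pulse 74, 10). The maximum rule still showed at most 0.25% as Low.

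**The case against.** **The rule does not hide every effect.** A reader might infer that the table would show no hypotension or bradycardia whatever the drug does. The last two rows of the table refute that: large sustained falls do appear, diastolic falls most readily. A patient with very few readings, or with persistently Low values, would also be shown as Low. This stands and limits the claim.

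**Low values are reported elsewhere.** A reader might also infer that the overall safety conclusion would be wrong. The documents do not support that. Part A SAP 3.8 includes the minimum in continuous summaries, so low readings reach the by-visit tables. The listing shows every out-of-range patient, 5.5.8 summarises ECG heart rate, and 5.5.1 tabulates adverse events. Protocol 10.10.3 asks for listings, flags and descriptive statistics; it requires no shift table. All of this stands. What is missing is a tabulated count.

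**A minimum has its own noise.** The no-effect row shows that a minimum over 13 visits classes up to about a quarter of patients as Low on diastolic pressure by chance, and Part A has no control arm. That is a reason to read such a table descriptively. It does not make the maximum suitable for the Low column.

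**The laboratory comparison is weak.** The sentence in 5.5.6 on maxima and minima is separate from the one on laboratory shift tables, which does not say which post-baseline value is used. It cannot be taken to show that laboratory shift tables use both. The ECG and physical-examination wording is the better comparison. It also makes it hard to read *maximum* as a loose word for *worst*, since the SAP uses both terms.

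**Table shells are in a separate document** and may differ. The SAP text, however, names only the maximum.

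**Conclusion.** The rule in Part A SAP 5.5.7 is wrong as written for the Low category. With no drug effect, at most about 0.01% of patients not Low at baseline would be shown as Low, against 2–24% with at least one Low reading, depending on the parameter and the correlation. With a sustained 10-unit fall, at most 4.7% would be shown, against 16–85%. Means, SDs, correlations and the normal model are assumptions; the direction does not depend on them.

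The consequence is a misleading Low column and no tabulated incidence of falls. No data are lost, and the other planned output would still carry low readings. The point applies to Part A only, because the Part B SAP already looks in both directions. It should be corrected, but it does not undermine the Part A safety analysis as a whole.

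**What to change.** In 5.5.7, replace the single shift table with two for each of systolic pressure, diastolic pressure and pulse: baseline to minimum post-baseline, read for shifts to Low, and baseline to maximum post-baseline, read for shifts to High. This matches the two-sided flags in protocol 10.10.3. The lower pulse limit should be reconciled at the same time, since the protocol flags resting heart rate below 40 and the SAP range starts at 50.

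The Part B SAP (1.1) says the Part A main period was completed at a 4 May 2021 cutoff and a study report prepared. If that report is final, issue the minimum-based table as a supplementary table, labelled as added afterwards.

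The cost is one more table per parameter from data already collected, and one sentence of SAP text if it is still open. The downside is that a minimum over many visits will class some patients as Low by chance, so a footnote should say that the table is descriptive and has no control arm.

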5.5.9 Physical Examinations

Physical examinations are performed as specified in the Schedule of Assessments (Table 3 and Table 6 Table 4).

At the screening visit, a complete physical examination consists of checking the normality or abnormality of the following body systems: general appearance, skin, eyes, ears, nose, throat, heart, chest/breast, abdomen, neurological system, lymph nodes, spine (skeletal), and extremities.

At other visits, an abbreviated physical examination consists of checking the normality or abnormality of the following body systems: general appearance, skin, abdomen, and cardiorespiratory examination.

Shift from baseline tables will be provided for general appearance, skin, abdomen, and cardiorespiratory examination for the worst post-baseline finding.

Patient data listings will be provided for patients with abnormal CS findings at any visits.

5.5.10 Online Cognitive Testing

Online cognitive tests are performed by using the Cogstate computerized battery at visits as specified in the Schedule of Assessments (Table 3 and Table 6). The four test domains are: Detection test; Identification test; One Back Working Memory Test and One Card Learning Test.

A separate SAP will be created by Cogstate and the cognitive testing results will be summarized in a separate report.

6 SUPPORTING DOCUMENTS

ITP Disease Activity – ITP-BAT Bleeding Assessment ITP-BAT BLEEDING SCALE

Assess how much bleeding the subject has at the following sites by physical examination and record the severity at each site below

Site	0	1	2
Skin (Physical Examination (PE))	☐ None☐ Not Done	☐ 1–5 bruises and/or scattered petechiae	>5 bruises with size >2 cm and/or diffuse petechiae
Oral (PE)	☐ None ☐ Not Done	1 blood blister or >5 petechiae or gum bleeding that clears easily with rinsing	☐ Multiple blood blisters and/or gum bleeding

Ask the subject to assess how much bleeding they have experienced over the previous week at the following nine anatomical sites and check the box that represents each answer

Site	0	1	2
Skin (Hx)	None	1–5 bruises and/or	>5 bruises with size >2 cm
		scattered petechiae	and/or diffuse petechiae
Oral (Hx)	☐ None	1 blood blister or	☐ Multiple blood blisters
	☐ Not Done	>5 petechiae and/or	and/or gum bleeding >5 min
		gum bleeding <5 min	
Epistaxis	□ None	☐ Blood when blowing	☐ Bleeding >5 min (per
	☐ Not Done	nose and/or epistaxis	episode)
		<5 min (per episode)	
Gastrointestinal (GI)	None	Occult blood	☐ Gross blood
	☐ Not Done		
Urinary (U)	□ None	Microscopic	☐ Macroscopic
	☐ Not Done	(+ve dipstick)	
Gynecological	☐ None (normal	☐ Spotting not at time	☐ Bleeding >spotting not at
(GYN)	period)	of normal period	time of period or very heavy
	□ Not Done		period
Pulmonary	None	□ N/A	☐Yes
	☐ Not Done		
Intracranial	None	□ N/A	Yes
haemorrhage	☐ Not Done		
Subconjunctival	None	Yes	□ N/A
haemorrhage	☐ Not Done		

General Quality of Life Evaluation: EQ-5D-5L

EuroQOL-5 Dimension 5 Level (EQ-5D-5L) (Feng 2015)

EQ-5D-5L descriptive system

[figure not shown]
Under each heading, please tick the ONE box that best describes your health TODAY

MOBILITY	
I have no problems in walking about	
I have slight problems in walking about	0
I have moderate problems in walking about	O.
I have severe problems in walking about	
I am unable to walk about	
SELF-CARE	
I have no problems washing or dressing myself	0
I have slight problems washing or dressing myself	D
I have moderate problems washing or dressing myself	0
I have severe problems washing or dressing myself	D
I am unable to wash or dress myself	D
USUAL ACTIVITIES (e.g. work, study, housework, family or leisure activities)	
I have no problems doing my usual activities	0
I have slight problems doing my usual activities	•
I have moderate problems doing my usual activities	.0
I have severe problems doing my usual activities	
I am unable to do my usual activities	D
PAIN / DISCOMFORT	
I have no pain or discomfort	
I have slight pain or discomfort	
I have moderate pain or discom	0
I have severe pain or discomfort	0
I have extreme pain or discomfort	Д
ANXIETY / DEPRESSION	
I am not anxious or depressed	
I am slightly anxious or depressed	
I am moderately anxious or depressed	0
I am severely anxious or depressed	· O
I am extremely anxious or depressed	

The EQ-VAS in EQ-5D-5L [31]

- We would like to know how good or bad your health is TODAY.
- . This scale is numbered from 0 to 100.
- 100 means the best health you can imagine.
 0 means the worst health you can imagine.
- . Mark an X on the scale to indicate how your health is TODAY.
- Now, please write the number you marked on the scale in the box below.

YOUR HEALTH TODAY =

We would like to know how good or bad your health is TODAY.

- . This scale is numbered from 0 to 100.
- 100 means the best health you can imagine.
 0 means the worst health you can imagine.
- Mark an X on the scale to indicate how your health is TODAY.
- Now, please write the number you marked on the scale in the box below.

YOUR HEALTH TODAY =

The best health

The worst health you can imagine

[©] EuroQol Research Foundation. EQ-5D* is a trade mark of the EuroQol Research Foundation

1 INTRODUCTION

1.1 STUDY DESIGN

Study PRN1008-010 (also known as DFI17124) is a 2-part, open-label Phase1/2 study investigating rilzabrutinib in participants with immune thrombocytopenia (ITP) who have relapsed or have an insufficient response to prior therapies. Part A (the dose finding part) of the main 24-week treatment period has been completed based on data cutoff date of 04 May 2021, and a clinical study report (CSR) has been prepared. Part B will investigate the safety and efficacy of rilzabrutinib 400 mg BID. Participants from both parts (A and B) may enter a common long-term extension (LTE). This SAP will cover Part B only.

Part B consists of a 28-day screening period, 24-week 400 mg BID rilzabrutinib active treatment period, and a long-term extension (LTE) period. There will be a 4-week safety follow-up period after the last dose of rilzabrutinib. All visits to be conducted are specified in the schedule of assessments of the protocol.

1.2 OBJECTIVES AND ENDPOINTS

Table 2 - Objectives and endpoints

Table 2 - Objectives and endpoints				
Objectives		Endpoints		
Primary	Primary			
Efficacy				
•	To further explore the clinical activity and durability of response of the selected dose of 400 mg BID of rilzabrutinib in participants with ITP who have relapsed or have an insufficient response to prior therapies	•	Proportion of participants able to achieve platelet counts ≥50,000/µL on at least 8 out of the last 12 weeks of the 24-week treatment period without the use of rescue medication after 10 weeks of active treatment	
Safety				
•	To characterize the safety and tolerability of 400 mg BID dose of rilzabrutinib in participants with ITP	•	The incidence, severity, and relationship of treatment- emergent adverse events (TEAEs), including clinically significant changes in physical examination, laboratory tests, electrocardiogram(s) (ECG(s)), and vital signs	
		•	TEAEs in the post treatment follow-up period and their possible relationship to prior rilzabrutinib treatment	
Second	-			
Efficacy				
•	To further explore the clinical activity and durability of response of the selected dose of 400 mg BID of rilzabrutinib in participants with ITP who have relapsed or have an insufficient response to prior therapies	•	Number of weeks with platelet count ≥50,000/µL OR ≥30,000/µL and doubling the baseline in the absence of rescue therapy (platelet counts will be censored for 4 weeks after the use of rescue medication, if given) Proportion of all treated participants able to achieve	

Property of the Sanofi group - strictly confidential

Page 6

two or more consecutive platelet counts, separated by at least 5 days of ≥50,000/µL AND an increase of

- platelet count of ≥20,000/µL from baseline without use of rescue medication in the 4 weeks prior to the latest elevated platelet count
- Number of weeks with platelet counts ≥30,000/µL and doubling from baseline over the 24-week treatment period (platelet counts will be censored for 4 weeks after the use of rescue medication, if given)
- Proportion of participants receiving rescue medication
- Change from baseline in ITP Bleeding Scale (IBLS)

Pharmacokinetic (PK)

 To characterize the pharmacokinetics of rilzabrutinib in participants with ITP

Plasma PK parameters of rilzabrutinib in ITP participants will be evaluated in each participant based on sparse sampling and population PK modeling

[figure not shown]
treatment and demonstrated a platelet response

Proportion of participants who completed 24 weeks of

defined as platelet counts ≥50,000/µL at 4 out of the

Exploratory

 To further explore the clinical activity and durability of response of the selected dose of 400 mg BID of rilzabrutinib in participants with ITP who have relapsed or have an insufficient response to prior therapies

